1.3 Secondary Objectives

- 1. To estimate the progression free survival distribution and to summarize the best tumor responses observed prior to progression or recurrence.
- 2. To explore the plasma pharmacokinetics (PK) of ABT-888 during ABT-888 and radiation therapy.
- 3. To explore peripheral blood mononuclear cell (PBMC) PARP activity before and after treatment with ABT-888.
- 4. To explore quantifying non-homologous end-joining (NHEJ) activity or γ -H2AX levels (as surrogate markers of unrepaired DSBs) in PBMC before and after treatment with ABT-888.
- 5. To explore quantifying PARP activity and DNA repair protein levels in biopsied atypical pontine gliomas, if available.
- 6. To explore associations of molecular parameters from secondary aims 3, 4 and 5 with PFS and OS after conclusion of clinical trial.
- 7. To explore the quantitative MR measures of relative cerebral blood volume (rCBV), vascular permeability (Ktrans, vp, and ve values), and apparent diffusion coefficient (ADC) within the first six months of initiating protocol treatment to correlate with disease outcome and determine whether such metrics differentiate patients with pseudoprogression from those with true early progressive disease.
- 8. To explore the potential utility of urine biomarkers as a novel, non-invasive method of detecting and tracking changes in the status of pediatric brain stem gliomas.

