9.1.4 Urine Biomarkers

Participation in the urine biomarker study is strongly encouraged but optional.

9.1.4.1 *Sampling Strategy*

Urine will be collected at time of enrollment (pre-treatment), post ABT-888 plus radiation then at the time of each scheduled MRI. Urine will be collected throughout the time that each patient is receiving protocol treatment until disease progression.

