13.4.3 Urine Biomarkers

Comparison of Urine Biomarker Levels in Patients vs. Controls:

In order to determine whether the levels of these urinary biomarkers are elevated in DIPG patients, we will compare median levels for tumor patients to levels in healthy age- and gendermatched controls using the Mann-Whitney U-test. Despite the presence of matched controls, Mann-Whitney U-test allows us to utilize a conservative approach compared to the Wilcoxon signed-rank test since matching by age and gender is done to reduce variability rather than to facilitate the use of methods for paired data. In addition, the percentage of patients and controls above the previously established cut-off values for each urinary biomarker will be compared using the chi-square test. Based on a preliminary power analysis for this chi-square test a sample

size of 58 brain tumor patients and 58 controls will provide 80% power with a conservative twosided alpha level of 0.01 in capturing a difference of 30% between the groups with respect to each urinary biomarker. We will also utilize ROC analysis for each biomarker in exploring various cut-points for differentiating between the control subjects and DIPG patients. Multivariable logistic regression models coupled with ROC analyses will be used to select a combination of these biomarkers in an attempt to improve their collective performance as a classifier.

Longitudinal Assessment of Changes in Biomarker Values and Their Association with Outcome: Using the data for patients who progress, for each biomarker we will compare the levels at baseline with levels at progression as determined by MRI to assess whether the biomarker values change and if so by how much. This will be done via Wilcoxon signed rank test and exact confidence interval estimates of the percent change. We will also tabulate the percentage of patients who have biomarker levels above the previously established cut points for each biomarker at baseline and at the time of progression. We will investigate whether the percentage of patients who are above/below the cutpoints for each of the biomarkers is different between baseline and time of progression via the McNemar's test. Provided adequate number of responses is present to make such analyses meaningful, we will also perform similar analyses comparing biomarker levels at baseline and at the time of response.

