Time-to-event data will be analyzed using the Kaplan-Meier product-limit method and by the log rank test to compare the PFS and OS distributions of patients with biomarker values above and below the specified cut-off values at baseline.⁵² Provided adequate number of events exist to make such an exercise informative, will also utilize multivariable Cox proportional-hazards regression model with each of the 8 urinary biomarkers as time dependent predictors and relevant covariates including age and gender to explore associations with PFS and OS.⁵³

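### The paired urine tests have no comparator, and no urine analysis compares responders with non-responders, so a shift common to all irradiated children can pass for a response marker.

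*Combined protocol and SAP*

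**What the plan says.** Secondary objective 8 (section 1.3) reads, up to its last word: "To explore the potential utility of urine biomarkers as a novel, non-invasive method of detecting and tracking changes in the status of pediatric brain stem". Section 2.4.4.3 gives as one aim to find out whether marker levels go along with changes in tumour status. On sampling, section 9.1.4 says: "Urine will be collected at time of enrollment (pre-treatment), post ABT-888 plus radiation then at the time of each scheduled MRI". Collection continues on protocol treatment until progression, and participation is optional.

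The longitudinal part of section 13.4.3 has three components:

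- **Progression, paired.** "Using the data for patients who progress, for each biomarker we will compare the levels at baseline with levels at progression as determined by MRI". On method: "This will be done via Wilcoxon signed rank test and exact confidence interval estimates of the percent change". The proportion of children beyond each cut-point is tested as "different between baseline and time of progression via the McNemar's test".
- **Response, paired.** Subject to enough responses, "we will also perform similar analyses comparing biomarker levels at baseline and at the time of response".
- **Outcome, between patients.** Kaplan-Meier and log-rank for PFS and OS by baseline marker level and, subject to enough events, a "multivariable Cox proportional-hazards regression model with each of the 8 urinary biomarkers as time dependent predictors" of PFS and OS.

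**The concern.** A paired test within one outcome group asks whether the marker moved. Objective 8 needs to know whether it moved differently in children whose disease status changed. Section 5.1.4.1 gives all enrolled children concurrent ABT-888 and radiation, and the baseline urine is taken before that. Within responders, or within progressors, the effect of treatment and elapsed time is therefore inseparable from the effect of status. A marker that falls in every child after radiation, whatever the tumour does, can produce a significant baseline-to-response change.

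What is at stake is specificity. A marker useful for following these tumours must stay put, or move less, in children without the status change, and the paired tests contain no such children. Elsewhere the plan allows for this kind of analysis: section 13.4.2.1 lets associations between the PBMC markers and objective response be explored. The urine section has no counterpart.

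**Working it through.** **1. The plan's own figure.** The only sizing figure in the urine section is 80% power with 58 patients and 58 controls, two-sided alpha 0.01, for a 30-point difference. The base rate is not given. Assuming 20% versus 50% (pooled variance, no continuity correction):

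n = [2.576 × √(2 × 0.35 × 0.65) + 0.842 × √(0.20 × 0.80 + 0.50 × 0.50)]² / 0.30² = (1.738 + 0.539)² / 0.09 ≈ 58 per group, power 80.4%.

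The figure reproduces, but it concerns patients versus controls. No figure is given for the longitudinal tests, so the rest is illustration.

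**2. Response: paired test against between-group test.** Assumptions not in the documents: 50 children with urine; 12 or 20 responders; normal log changes with SD 0.7 to 1.0; the same fall in all children, unrelated to response; 5% two-sided.

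Standardised shift = |ln(1 − fall)| / SD:
- 30% fall: 0.357/1.0 = 0.36 to 0.357/0.7 = 0.51
- 50% fall: 0.693/1.0 = 0.69 to 0.693/0.7 = 0.99

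Share of simulated studies with p < 0.05 (1,500 runs per cell):

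| Responders | Common fall | Signed-rank in responders | Mann-Whitney, responders vs the rest |
|---|---|---|---|
| 12 | 30% | 17-30% | 4-6% |
| 12 | 50% | 53-86% | 4-6% |
| 20 | 30% | 33-56% | 4-6% |
| 20 | 50% | 80-98% | 4-6% |

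Repeat runs moved single cells by up to about 4 percentage points. With 6 responders the paired test rejected in about 7-35% over the same range.

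**3. Progression: paired test.** Same idea, with the common shift in units of the SD of change. With 48 progressors the signed-rank test rejects in 39%, 91% and about 100% of runs at shifts of 0.25, 0.5 and 0.8 SD; with 30 progressors, in 27%, 74% and 99%.

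**4. Progression: the Cox model.** 58 children, 500 runs, assumed MRI times, PFS drawn independently of the marker, one marker in the model, SD of change √2 × 0.7 ≈ 1.0:

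| Common shift after baseline | Paired test in progressors | Time-dependent Cox, PFS |
|---|---|---|
| 0 | 6% | 6% |
| 0.5 | 94% | 5% |
| 1.0 | 100% | 6% |

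At each event the Cox model compares the progressing child with children still at risk, so a shift shared by all cancels. It has PFS and OS as outcomes and so has no such role for response.

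**The case against.** Four arguments can be made for the plan.

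- **The Cox model exists.** A reader might infer that urine change is examined only inside outcome groups. The documents do not support that for progression: the time-dependent Cox model is a between-patient analysis of PFS and OS. Its condition on events is likely to be met, since section 2.4.4.2 expects more than 80% of patients to progress within 1 year, unless few families join the optional urine study. This stands. What remains is that the plan does not say which result governs if the paired test and the Cox model disagree.
- **The paired tests claim only change.** Their stated purpose is whether values change and by how much, and there is no decision rule. A reader might infer that a non-specific marker will be reported as tracking disease; the text does not say so. This also stands, but the subsection heading announces association with outcome, and objective 8 invites that interpretation.
- **The response analysis is itself conditional**, and with few responders it seldom rejects (10% with 6 responders and a 0.5 SD shift). True, but the test would be run when responses are plentiful, which is when a false signal is most likely.
- **The size is assumed.** Responder numbers, shift, SD and alpha are not in the documents. The between-group rate near 5% follows from simulating no difference. Both are correct; the figures show the mechanism and are not a forecast.

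**Conclusion.** The signed-rank and McNemar analyses are uncontrolled before-after tests and cannot on their own support a statement that a marker follows response or progression. For response nothing else in the urine section fills the gap. For progression the time-dependent Cox model largely does, but it is contingent and is not designated for that purpose. Under the assumptions in the working, a marker carrying no information on response gives a significant paired result in roughly one study in six at the low end (12 responders, 30% fall, SD 1.0) and nearly all studies at the high end (20 responders, 50% fall, SD 0.7). That the paired test cannot tell the two explanations apart does not depend on those assumptions; how often it misleads does. The point is worth correcting because it is cheap, but it touches only an optional, exploratory correlative study.

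**What to change.** In section 13.4.3:

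1. State that the signed-rank and McNemar analyses are descriptive.
2. **Response.** Add a comparison of change from enrolment between responders and non-responders at the same scheduled MRI visit, for each visit at which response is assessed. One fixed visit will not do: sections 11.1.1 and 11.1.2 require response to last at least 8 weeks, section 13.2.2 uses best response before failure, and a response may first appear after week 10-11. Use a rank-based test on the change itself, or a log with a stated offset or detection-limit rule, because Table 6 shows tumour-group values of 0 for MMP-9, MMP-9/NGAL and MMP-2. For the cut-point version, compare proportions between the groups.
3. **Progression.** Name the time-dependent Cox model as the analysis that supports any statement that a marker tracks progression. A mixed model of the marker on progression status, with scheduled visit as a factor and a patient random effect, would also serve.

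**Cost.** Analysis wording and a little more work; no new patients or samples, since urine is already scheduled at these visits. Power is lower than for the paired test: with the assumed SDs, a true extra 30% fall in responders is detected in only 18-30% of studies (12 versus 38) or 22-37% (20 versus 30). Comparators also thin out at later visits, because collection stops at progression. The comparison may be inconclusive and should be labelled exploratory.

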2.4.4.1 Preliminary data

We reported the first demonstration of the utility of urinary biomarkers in brain tumors, including the use of molecules specifically related to the regulation of vascular stability⁴³ and recently published a proof-of-principle case series, that specifically evaluated the ability of a panel of urinary biomarkers such as MMP-2, MMP-9, NGAL and VEGF (See Figure 4 and **Table 6** and **Table 7**).⁴⁴ The results of this series support the premise that levels of urinary biomarkers can not only predict the presence of brain tumors but also that they change in response to effective surgical therapy (see Figure 5).

We have subsequently identified additional biomarkers that can be detected in urine in association with pediatric brain tumors. These new markers (HB-EGF, EGF, HGF and TIE-2) allow for greater sensitivity in identifying the presence of disease. Specific to this project, these markers have been evaluated in pediatric patients with various subtypes of high grade glioma, including both GBM and anaplastic astrocytoma.

Table 6								
Demographics, MMP's and VEGF for Brain Tumor Patients and Controls								
Variable	Contro	ol Group ((n=23)	Brain T	`umor Group	o (n=28)	Р	
	Median	IQR	Range	Median	IQR	Range		
Age, yr	22	4-55	0-71	32	8-58	1-73	0.37	
MMP-9	0	0-0	0-6	0.6	0-5.7	0-294	< 0.001*	
MMP-9/NGAL	0	0-0	0-12.8	0.8	0.2-1.0	0-1.1	< 0.001*	
MMP-2	0	0-0	0-3	4.3	0.8-8.8	0-27	< 0.001*	
VEGF	25	0-250	0-391	753	451-957	25-4462	< 0.001*	
Female sex, no. (%)	11(48)				13 (46)		0.92	

T 11 (

Table '	7
---------	---

Results of Receiver Operating Characteristic (ROC) Curve Analysis and Diagnostic Performance Indices of MMP-2 and VEGF							
	01 NIN	P-2 and VEGF					
Biomarker	AUC	95% CI	P value				
MMP-2 (ng/ml)	0.894	0.800-0.987	< 0.0001				
VEGF (pg/L)	0.965	0.913-0.999	<0.0001				
Cutoff Points	Sensitivity (95% CI)	Specificity (95% CI)	Accuracy (95% CI)				
MMP-2 >0.4 ng/ml	82.1 (65.2-94.0)	95.7 (78.1-99.9)	88.2 (76.1-95.6)				
VEGF >350 pg/L	95.2 (76.2-99.9)	89.5 (66.9-98.8)	92.5 (80.0-98.5)				

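### Urine cut-offs built to detect a tumour are reused to split DIPG patients for PFS and OS, which is likely to give unbalanced groups and low power, above all for VEGF

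*Combined protocol and SAP*

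**What the plan says.** Section 2.4.4.1, Table 7, is titled "Results of Receiver Operating Characteristic (ROC) Curve Analysis and Diagnostic Performance Indices of MMP-2 and VEGF". It gives two cut-offs from a comparison of brain-tumour patients with controls: MMP-2 >0.4 ng/ml (sensitivity 82.1%, 95% CI 65.2-94.0) and VEGF >350 pg/L (sensitivity 95.2%, 95% CI 76.2-99.9). Section 9.1.4.5 plans eight markers, with quantitative ELISA levels for all of them. The document prints no cut-off for the other six.

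Section 13.4.3 uses cut-offs in three places:

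- Patients against controls: "the percentage of patients and controls above the previously established cut-off values for each urinary biomarker will be compared using the chi-square test".
- Baseline against progression: a paired test of the share of participants "who are above/below the cutpoints for each of the biomarkers is different between baseline and time of progression via the McNemar's test".
- Survival: the Kaplan-Meier method and log-rank test are used "to compare the PFS and OS distributions of patients with biomarker values above and below the specified cut-off values at baseline".

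It plans two analyses that are not tied to a cut-off. Levels at baseline and at progression are compared first: "This will be done via Wilcoxon signed rank test and exact confidence interval estimates of the percent change". A multivariable Cox model with the eight markers as time-dependent predictors follows if there are enough events.

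**The concern.** A diagnostic cut-off suits the patient-control comparison. Within a cohort where everyone has the tumour, the share above the cut-off is its sensitivity, so a good diagnostic cut-off makes a poor dividing line between patients. No separate prognostic cut-off is given, and the search for new cut-points in 13.4.3 serves only to tell DIPG patients from controls.

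Two analyses are exposed. The survival comparison may set a handful of patients against all the rest. In McNemar's test, a rise registers only in a patient who starts below, so a patient already above counts as unchanged however far the level climbs. A null result from either could be read as evidence that the marker carries no information, which bears on secondary objective 8 (section 1.3).

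**Working it through.** **The plan's own figure.** The only sample-size statement is for the patient-control chi-square test: "size of 58 brain tumor patients and 58 controls will provide 80% power with a conservative twosided alpha level of 0.01". The effect assumed there is 30 percentage points. With n = [z(0.995)·√(2p̄q̄) + z(0.80)·√(p1q1 + p2q2)]² / 0.30² and p1 = 0.50, p2 = 0.80 (so p̄ = 0.65):

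n = (2.576 × 0.6745 + 0.8416 × 0.6403)² / 0.09 = 57.6, i.e. 58 per group.

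The figure reproduces. The base rates are inferred, because none is stated; 20% against 50% gives the same result. It says nothing about the survival or McNemar tests, for which no power is given.

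**Inputs for those tests**

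- Share above the cut-off, s: 0.952 (VEGF) and 0.821 (MMP-2), from Table 7. Table 6 agrees, if its units match: the tumour group's lower quartiles, 451 for VEGF and 0.8 for MMP-2, both exceed the cut-offs.
- Patients: 60, the approximate Phase II size in section 13.3. Participation is optional (section 9.1.4), so this may be generous.
- Deaths: 54, an assumption. Historical 24-month survival in Table 20 is 10.21%, and 60 × 0.898 = 53.9.
- Two-sided alpha 0.05, an assumption; none is stated for these tests.

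**Expected number below the cut-off**, 60 × (1 − s):

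- VEGF: 60 × 0.048 = 2.9
- MMP-2: 60 × 0.179 = 10.7

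**Log-rank power** = Φ(√(D·s(1−s))·ln HR − 1.96), with D = 54:

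| Split | s | D·s(1−s) | HR 2 | HR 3 |
|---|---|---|---|---|
| VEGF cut-off | 0.952 | 2.47 | 19% | 41% |
| MMP-2 cut-off | 0.821 | 7.94 | 50% | 87% |
| Equal groups | 0.500 | 13.50 | 72% | 98% |

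Over the printed sensitivity intervals, power at HR 2 is 58% (s = 0.762) down to 4% (s = 0.999) for VEGF, and 68% (s = 0.652) down to 23% (s = 0.940) for MMP-2. The normal approximation is rough with about three patients in a group. At s = 0.999 only 60 × 0.001 = 0.06 patients are expected below, so there would usually be nothing to compare. With 58 patients and 58 events, the HR 2 figures are 20%, 53% and 75%.

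**McNemar's test, rise at progression.** With k pairs all changing one way, the exact two-sided p is 2 × 0.5^k: 0.0625 for k = 5 and 0.031 for k = 6. At least six patients must therefore start below. The binomial chance that fewer than six do is:

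- VEGF: 93% at n = 60 and 99% at n = 40. At n = 60 this runs from 0.2% if the sensitivity is 76.2% to essentially 100% if it is 99.9%.
- MMP-2: 3% at n = 60.

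With 55 progressors (assumed), simulated power if every patient below moves above is about 5% for VEGF and 94% for MMP-2; if 80% of them do, MMP-2 has 82%. In the other direction, if 20% of those above drop below and no one rises, power is 97% for VEGF and 91% for MMP-2.

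**The case against.** A reader might infer that almost every patient lies above the cut-offs and that these analyses cannot show an effect. The documents do not support that. At best it describes VEGF. About 11 of 60 patients would fall below the MMP-2 cut-off, MMP-2 has 87% log-rank power at HR 3, and its McNemar test can register a rise. The MMP-9 lower quartile in Table 6 is 0, so roughly a quarter or more of that series would not exceed any non-negative cut-off. For the six markers without a printed cut-off nothing can be computed. McNemar's test could also detect a fall, and 13.4.3 plans similar comparisons at response.

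The sensitivities come from a small mixed-age series (28 tumour patients, median age 32), not from children with DIPG, and their intervals are wide. This stands, and it is why the results are given as ranges. At every value in those intervals, power at HR 2 is still below that of an even split.

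The 72% comparator assumes the hazard ratio at the median equals that at the diagnostic cut-off. These are different contrasts, so 72% is a benchmark and not a measured loss.

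A reader might also infer that the trial would miss a change at progression. It need not: the signed-rank test and percent change come first in 13.4.3 and use levels, so a further rise in an already-high patient is captured.

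Finally, the Cox model may well run, since events should be plentiful. But it is conditional, multivariable and uses time-dependent values. It does not ask whether the baseline level predicts outcome. The only unconditional analysis of that question is the log-rank test split at the cut-off.

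**Conclusion.** The concern holds for the baseline survival comparison, most clearly for VEGF. If Table 7 carries over to DIPG, the split is about 3 against 57 for VEGF and 11 against 49 for MMP-2, with power at HR 2 of about 19% (4-58%) and 50% (23-68%). These figures rest on 60 participants, 54 deaths and two-sided 0.05. For change at progression the problem is minor: McNemar's test is almost uninformative for a rise in VEGF at the point estimate, much less so for MMP-2, and the signed-rank test already covers the question. This is an exploratory, optional substudy. The primary OS result and the patient-control comparison are not affected.

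**What to change.** In section 13.4.3:

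1. For PFS and OS, make the main analysis a Cox model of each marker's baseline ELISA level as a continuous covariate. Use a transform that allows zeros, for example log(x+1) with the unit fixed in advance, or ranks; Table 6 shows zero values for MMP-2 and MMP-9, so a plain log will not do. Show Kaplan-Meier curves split at the cohort median for display, and keep the diagnostic cut-off log-rank test as descriptive.
2. For change at progression, name the planned Wilcoxon signed-rank test and percent change as the main analysis and label McNemar's test descriptive.
3. Keep the diagnostic cut-offs for the patient-control comparison, and state them for the remaining six markers or say that none exists.

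The cost is a change of wording, because ELISA levels are already planned for all eight markers. The downside is that the survival results will be less directly tied to the published diagnostic cut-offs.
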